8. STUDY OUTCOME MEASURES

8.1. Primary Endpoints

Primary end points included new onset symptomatic thrombosis requiring medical or surgical intervention or death due to thrombosis defined as fatal PE, ischemic

Sponsor: Minapharm Pharmaceuticals
Protocol Number: Sub-Thromb-001
Version: 1 amendment 1

stroke, mesenteric thrombosis, or myocardial infarction.

The number of clinical PE events will be measured by spiral CT

Mean changes in APTT where it will be done before first dose, 4 & 8 hours after first dose then on days 1,8,15 post operatively

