Clinical & laboratory investigations	
For Events of Deep Vein Thrombosis (DVT) within 15 days post-op.)
 
All of the patients underwent Routine bilateral compression Doppler.
 
For Clinical PE (Pulmonary Embolism) Events from Day of surgery and During Hospitalization period or end of study
 
Clinical PE events PE (Pulmonary Embolism) events were confirmed by spiral CT.
 
For follow up:
 
APTT should be done before the first dose then after 4 & 8 hours of the first dose, then on days 1,8,15 post operatively.

Study duration	
Enrolment period: 3 months duration
 
Follow-up duration: Follow-up per patient will be for a period of 15 days

Eligibility Criteria	
Inclusion Criteria:
 
 18 years of age or older Body Weight >60 kg Patients undergoing major orthopedic operations

	
Patients ready to sign informed consent form (ICF) Patients should discontinue any agents that affect haemostasis prior to the study medication use unless strictly indicated. These agents include medications such as: anticoagulants, thrombolytics, non-steroidal anti-inflammatory agents (including Ketorolac tromethamine), preparations containing aspirin, systemic salicylates, ticlopidine, dextran 40, clopidogrel, other anti-platelet agents including glycoprotein IIb/IIIa antagonists or systemic glucocorticoids.
 
Exclusion Criteria:
 
Significant bleeding injury such as solid organ laceration or intracranial bleed at discretion of attending physician Hypersensitivity to Hirudin or prior documented Allergy to its components Pregnant or breast feeding Hemorrhagic stroke in preceding 3 months abnormal baseline coagulation characterized by an INR >1.4, obtained at the discretion of the treating clinician Required therapeutic anticoagulation for atrial fibrillation, prior VTE, or mechanical heart valve Patients with a history of coagulation disorder Treatment with concomitant anti-platelet agent other than aspirin 326 mg or more daily (Platelet count < 100 X10⁹ /dl) Active bleeding Subjects with a life expectancy less than 1 month

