Statistical analysis	
- Descriptive analysis: All statistical tests used a significance level of P=0.05, two tailed tests are performed for all analyses used statistical testing. Descriptive analysis for quantitative data will include count, mean with 95% CI, standard deviation, median, minimum and maximum. For qualitative categorical variables; frequency and percentage and 95% confidence interval will be applied.

Stopping rules	
DVT PE Major bleeding Allergy APTT value increases by 2-2.5 folds According to investigator evaluation

Table of Contents

Title Page	1
1. Synopsis	2
Table of Contents	6
2. LIST OF ABBREVIATIONS	9
3. SIGNATURE(S) PAGE	10
4. INTRODUCTION	11
4.1. Background	11
4.2. Correlative studies:	11
4.3. Study Rationale	12
5. STUDY OBJECTIVES	12
5.1. Primary Objectives	12
5.2. Secondary objectives	12
6. TRIAL DESIGN	12
6.1. The pre-operative Phase	12
6.2. The operative Phase	13
6.3. The Follow-up Phase	13
7. FLOW CHARTS:	13
7.1. STUDY FLOW CHARTS:	13
7.2. STUDY PHASES	14
8. STUDY OUTCOME MEASURES	15
8.1. Primary Endpoints	15
8.2. Secondary Endpoints	16
9. STUDY POPULATION	16
9.1. Recruitment strategy:	16
9.2. Inclusion Criteria	16
9.3. Exclusion Criteria	16
10. STUDY PROCEDURE:	17
10.1. Selection of the study population:	17
10.2. Case Report Form	17
11. SOURCE DATA	17

12.	TREATMENT OF TRIAL PARTICIPANTS	18
12.1.	Description of Study Medication(s)	18
12.2.	Concomitant Medication (if applicable).....	19
13.	DATA COLLECTION	19
15.1.	DATA MANAGEMENT	20
15.2.	AMENDMENT TO THE PROTOCOL.....	20
15.2.1.	Protocol Deviations	20
15.2.2.	Onsite Audits.....	20
15.2.3.	Study Monitoring	21
15.3.	PREMATURE DISCONTINUATION OF STUDY.....	22
16.	SAFETY REPORTING AND DEFINITIONS	22
16.1.	Adverse Events Monitoring.....	22
16.2.	Reporting Period.....	23
16.3.	Adverse Event (AE):	23
16.4.	Serious Adverse Events	24
16.4.1.	Instructions for Reporting Serious Adverse Events	24
17.	STATISTICAL METHODOLOGY	24
17.1.	Determination of Sample Size.....	24
17.2.	Analysis Variables:.....	25
17.2.1.	Primary analysis variables:.....	25
17.2.2.	Secondary analysis variables:.....	25
17.2.3.	Statistical Method:.....	25
17.2.4.	Interim Analysis	25
18.	ETHICS.....	25
18.1.	INDEPENDENT ETHICS COMMITTEE (IEC) OR INSTITIUTIONAL REVIEW BOARD (IRB).....	25
18.2.	Ethical principles:	26
18.3.	Laws and regulations:	26
18.4.	PATIENT INFORMATION AND CONSENT	26
18.5.	DISCONTINUATION OF THE STUDY	27
18.5.1.	PREMATURE DISCONTINUATION OF STUDY	27

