4. INTRODUCTION

4.1. Background

Hirudin is the most potent naturally-occurring direct thrombin inhibitor (DTI), and the first parenteral anticoagulant used on humans.¹

Originally derived from the medicinal leech (*Hirudo medicinalis*), it consists of a 65 amino acids polypeptide chain, forming non-covalent, equimolar, non-reversible 1:1 complexes with α thrombin.¹ When hirudin-bound, thrombin-catalyzed reactions and fibrinogen clotting are blocked, and coagulation is subsequently inhibited.² Hirudin was previously produced in limited amounts, however, recombinant DNA technology allowed its mass production.³ These recombinant forms bind bivalent to thrombin with pharmacokinetic and anticoagulant profile similar to that of the native form.⁴

Recombinant Hirudin is a direct inhibitor of thrombin. It binds in 1:1 ratio with thrombin thus blocking the coagulation cascade and the formation of thrombi.⁵

Unlike heparins, the action of Hirudin is totally independent from any coagulation cofactor that may interfere or alter its action.⁵

Thrombexx is useful in the prevention of thromboembolic complications in at risk patients thrombexx (15 mg) is administered by subcutaneous injection 5-15 minutes before orthopedic or general surgery (after induction of regional block anesthesia) then 15 mg twice daily for 9-12 days and in bedridden patients until patient is fully ambulant (maximum 12 days)⁵

According to the FDA Therapeutic Equivalence Evaluation, 30th Edition, the biosimilar of recombinant hirudin, Desirudin is FDA approved, therefore, the same applies to recombinant hirudin in Egypt.

4.2. Correlative studies:

- 1- Study of Prevention of Thromboembolic with Use of Recombinant Hirudin, Results of a Double-Blind, Multicenter Trial Comparing the Efficacy of Desirudin (Revasc) with That of Unfractionated Heparin in Patients Having a Total Hip Replacement⁶ which showed that desirudin to be more effective than heparin in the prevention of deep vein thrombosis, without any increase in the requirements for transfusion or the risk of hemorrhage. The prevalences of over-all and proximal deep-vein thrombosis in the 174 patients who had been managed with desirudin and were included in the per-protocol analysis were 7 and 3 per cent (thirteen and six patients), respectively.⁶

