5. STUDY OBJECTIVES

5.1. Primary Objectives

To evaluate the efficacy of Subcutaneous Thrombexx® ampoules (r-Hirudin RB variant 15 mg) in DVT prophylaxis post major orthopedic operations

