17. STATISTICAL METHODOLOGY

17.1. Determination of Sample Size

Sample size: Records for 100 patients who underwent major orthopedic surgery collected from 1 site

The sample size is based on literature review for previous studies, and a sample of 168 patients will be sufficient to detect an incidence of 12.5% of DVT with an acceptable error of 5%, and a 95% confidence level

17.2. Analysis Variables:

17.2.1. Primary analysis variables:

Proportion of patients experienced new onset symptomatic thrombosis
The number of clinical PE (Pulmonary Embolism) events will be measured by spiral CT

17.2.2. Secondary analysis variables:

Number of adverse events recorded
Proportion of patients experienced major bleeding

17.2.3. Statistical Method:

Descriptive analysis:

All statistical tests used a significance level of $P=0.05$, two tailed tests were performed for all analyses used statistical testing.

Descriptive analysis for quantitative data will include count, mean with 95% CI, standard deviation, median, minimum and maximum. For qualitative categorical variables; frequency and percentage and 95% confidence interval will be applied.

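### The primary endpoint text, the DVT objective, the planning rate and SAP Table 8 do not describe one event, so a symptom-free DVT found on routine Doppler is a non-event by definition but an abnormal result in the primary table

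*Protocol*

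**What the plan says.** **Objective.** Protocol 5.1 sets out to evaluate efficacy "in DVT prophylaxis post major orthopedic operations". SAP 3.1 repeats this.

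**Endpoint.** The protocol synopsis, protocol 8.1 and SAP 4.1 give the clinical endpoint: "Primary end points included new onset symptomatic thrombosis requiring medical or surgical intervention or death due to thrombosis". Protocol 8.1 and SAP 4.1 add two further primary items: "The number of clinical PE events will be measured by spiral CT", and mean APTT change.

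**Analysis variable.** Protocol 17.2.1 and SAP 8.2.1 list "Proportion of patients experienced new onset symptomatic thrombosis", followed by the count of clinical PE.

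**Measurement.** The synopsis entry on investigations says: "All of the patients underwent Routine bilateral compression Doppler". Protocol 7.2 places the Doppler at the Day 1, Day 8 and Day 15 visits.

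**Planning rate.** Protocol 17.1 and SAP 8.1 say that 168 patients are "sufficient to detect an incidence of 12.5% of DVT", with 5% error and 95% confidence. The same sections give the sample as 100.

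**Display.** SAP Table 8 has the symptomatic-thrombosis title. Its rows ask whether a Doppler was done, whether the report was signed, and whether the result was normal or abnormal, by visit. No row covers symptoms, intervention or death.

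**Stopping.** The synopsis entry on stopping rules reads: "DVT PE Major bleeding Allergy APTT value increases by 2-2.5 folds According to investigator evaluation". Protocol 15.3 names DVT among the events for which the sponsor may end the trial. Protocol 18.5.1 repeats that termination list without naming DVT.

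**The concern.** The trial systematically measures what its objective names, which is DVT, and then defines its primary event by something narrower. Take a patient with no symptoms whose Day 8 scan shows a DVT. Under 8.1 and 17.2.1 this patient has no primary event, and the PE and APTT items do not capture the DVT either. Under Table 8 the same patient is abnormal in the primary efficacy table. No text in either document says which applies.

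Two different headline results can therefore be reported from the same data, both under the title of symptomatic thrombosis, and the choice could be made after the results are known. The trial has a single arm, so no control rate would expose the difference. A low symptomatic rate could be read as successful DVT prophylaxis while Doppler-proven DVTs were present.

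**Working it through.** **1. The same event under each part of the plan**

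| Place | Event described | Symptom-free DVT on a scheduled scan |
|---|---|---|
| Protocol 5.1, SAP 3.1 | DVT | relevant |
| Protocol 8.1 and 17.2.1, SAP 4.1 and 8.2.1 | symptomatic thrombosis needing intervention, or thrombotic death | not an event |
| Protocol 17.1, SAP 8.1 | DVT, not limited to symptomatic | not excluded by the wording |
| SAP Table 8 | abnormal Doppler | shown as abnormal |

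**2. The plan's own figure.** With n = z² p(1 − p)/d², p = 0.125, d = 0.05 and z = 1.96:

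1.96² × 0.125 × 0.875 / 0.05² = 168.07

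The stated 168 is reproduced, from a rate given for DVT. It does not yield 100; that mismatch is a separate matter. At n = 100 the half-width is 1.96 × √(0.125 × 0.875/100) = 6.5 percentage points.

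**3. How far the two readings can differ in 100 patients.** Let s be the share of DVTs that are symptomatic. The documents give no value, so s = 10% to 30% is an assumption. The counts cover DVT only; other thrombosis and thrombotic deaths would add to them.

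- Any DVT: 100 × 0.125 = 12.5 expected. If 12 were observed, the exact 95% CI would be 6.4% to 20.0%.
- Symptomatic DVT: 12.5 × 0.10 = 1.25, to 12.5 × 0.30 = 3.75.
- Chance of no symptomatic DVT: (1 − 0.0125)^100 = 28%, to (1 − 0.0375)^100 = 2%.
- If 0/100 were observed, the exact 95% upper limit would be 1 − 0.025^(1/100) = 3.6%.

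**4. The same with the rate cited in protocol 4.2.** That section gives "The prevalences of over-all and proximal deep-vein thrombosis in the 174 patients who had been managed with desirudin" as thirteen and six patients. Overall, 13/174 = 7.5%. In 100 patients this is about 7.5 DVTs, of which 0.75 to 2.24 would be symptomatic under the same assumption, and the chance of none is 47% to 10%.

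**5. If acting on a scan averts later symptoms.** Suppose that half of the symptomatic DVTs in step 3 are averted (an assumption). Then 1.25 × 0.5 = 0.6 to 3.75 × 0.5 = 1.9 remain. If all are averted, none remain.

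**The case against.** The strongest reply is Table 8 itself. A reader might infer from 8.1 that scan-detected DVTs drop out of the primary result. The documents do not support that as a settled fact, because Table 8, the only SAP display for this variable, would show each of them as abnormal. This stands. What is established is a conflict between definition and table. Table 8 does not cure it, since it omits symptoms, intervention and death, and it reports by visit rather than per patient.

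A reader might also infer that a DVT on a scan stops the patient's drug, leads to treatment, and so prevents the symptomatic event from being counted. No passage says this. The synopsis list gives neither level nor action, and 15.3 concerns the sponsor ending the trial. A DVT already symptomatic when scanned would still count. Interception is a plausible inference, and nothing in the plan rules it out: neither document says how outcomes after a stop are handled.

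Protocol 6.3 can be read as using Doppler only to confirm a DVT that has already appeared, and 7.2 labels the scan as confirmation. The synopsis statement that all patients were routinely scanned outweighs this, but the wording is loose.

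Finally, a symptomatic endpoint is a legitimate choice, and the second cited desirudin trial used similar wording. It would be coherent if the objective, planning rate and table matched it. They do not. Setting the two cited trials side by side would not show how many DVTs are missed here, because the documents do not give the second trial's size or population.

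**Conclusion.** The point holds as an inconsistency in what the primary event is. Objective, planning rate and Table 8 point to DVT; the endpoint and the analysis variable point to symptomatic thrombosis or thrombotic death. No text classifies a symptom-free DVT seen on Doppler. Until one does, the primary proportion is not a single defined quantity, and the symptomatic-only version cannot by itself answer the stated objective.

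At the plan's 12.5% rate the readings differ by about 12.5 against 1.25 to 3.75 DVT events per 100 patients. The first figure follows from the documents; the second rests on the assumed symptomatic share of 10% to 30%. A further downward bias from acting on scan findings is possible but inferred, and its size is unknown. The definition should be settled before the data are analysed.

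**What to change.** In the protocol synopsis, 8.1 and 17.2.1, and in SAP 4.1 and 8.2.1, define the primary event per patient through Day 15 as any of:

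- Doppler-confirmed DVT, symptomatic or not, on a scheduled or unscheduled scan;
- any other symptomatic thrombosis requiring intervention;
- clinical PE confirmed by CT;
- thrombotic death.

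Rebuild SAP Table 8 as the proportion of patients with an event, with an exact 95% CI. Show symptomatic DVT, asymptomatic DVT and the present symptomatic-only definition as separate lines. State in protocol 17.1 and SAP 8.1 which event the 12.5% refers to.

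Add an analysis rule that a patient with a confirmed DVT counts as an event whether or not treatment or follow-up then stops. The sponsor must reconcile the stopping passages (the synopsis, 15.3 and 18.5.1) on whether they act on the patient or the trial, and on whether DVT is included. No clinical rule is proposed here.

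The cost is wording and one table, since the scans are already scheduled. The downside is a reported event rate that is higher, and so looks less favourable, than the symptomatic-only rate.

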2.3 The Follow-Up Phase

During this phase which is approximately 15 days, PE (Pulmonary Embolism) which is confirmed by spiral CT chest, any new DVT appears also to be confirmed by Doppler ultrasound, Bleeding assessment, APTT will be done on days 1, 8 & 15, concomitant medications, Hospital stay and any adverse event data will all be recorded

3 Study Objective:

3.1 Primary Objectives:

- To evaluate the efficacy of Subcutaneous Thrombexx® ampoules (r-Hirudin RB variant 15 mg) in DVT prophylaxis post major orthopedic operations

3.2 Secondary Objectives:

- To evaluate the safety of Subcutaneous Thrombexx® ampoules (r-Hirudin RB variant 15 mg) in DVT prophylaxis post major orthopedic operations in terms of serious bleeding.
- Predictive factors; baseline characteristics, Thrombexx® dose, duration and concomitant medications.
- Study population demographics and characteristics.

4 Study Outcome Measures:

4.1 Primary Endpoints:

- Primary end points included new onset symptomatic thrombosis requiring medical or surgical intervention or death due to thrombosis defined as fatal PE, ischemic stroke, mesenteric thrombosis, or myocardial infarction.
- The number of clinical PE events will be measured by spiral CT
- Mean changes in APTT where it will be done before first dose, 4 & 8 hours after first dose then on days 1,8,15 post operatively

4.2 Secondary Endpoints:

- **Major Bleeding:** was defined as clinically evident hemorrhage associated with a hemoglobin decrease ≥ 2 g/dL that leads to a transfusion of ≥ 2 units of whole blood or packed red cells outside of the perioperative period (time from the start of the surgery or procedure and up to 12 hours after), or hemorrhage that is intracranial, retroperitoneal, or into a prosthetic joint.

- Number of any reported (AE) or (SAE) during the study duration.

5 Study Population

This is a prospective study, it is important to have a well-defined study population in place prior to the start of the study. Study populations should be defined using specific inclusion and exclusion criteria, which will be used to evaluate a potential subject's ability to participate in the study.

5.1 Recruitment strategy:

It is essential that the recruitment process take into account factors that will optimize the type and number of participants enrolled in the study while minimizing time and expense. Failure to meet target accrual goals can affect the "power" of a study, making it less successful in providing quality results.

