8.2 Analyses variables

8.2.1 Primary analysis variables:

- Proportion of patients experienced new onset symptomatic thrombosis
- The number of clinical PE (Pulmonary Embolism) events will be measured by spiral CT

8.2.2 Secondary analysis variables:

- Number of adverse events recorded
- Proportion of patients experienced major bleeding

8.2.3 Statistical Method:

Descriptive analysis:

All statistical tests used a significance level of $P=0.05$, two tailed tests were performed for all analyses used statistical testing.

Descriptive analysis for quantitative data will include count, mean with 95% CI, standard deviation, median, minimum and maximum. For qualitative categorical variables; frequency and percentage and 95% confidence interval will be applied.

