9.2 Primary End Point

Table 8 *Proportion of patients experienced new onset symptomatic thrombosis*

		Follow-up 1 (Day 1)	Follow-up 2 (Day 8)	Follow-up 3/ End of Study (Day 15)	p-value
Was a Routine bilateral compression Doppler done?	Yes, N (%)				
	No, N (%)				
If “No”, please indicate a reason	Reason 1, N (%)				
	Reason 2, N (%)				
	Reason 3, N (%)				
Is the report interpreted, signed & dated by the PI or any of the designated site staff?	(Yes), N (%)				
	(No), N (%)				
If “No”, please indicate a reason:	Reason 1, N (%)				
	Reason 2, N (%)				
	Reason 3, N (%)				
If “Yes”, the report interpretation shows that the subject is:	Normal, N (%)				
	Abnormal, N (%)				
If abnormal, please state the reason:	Reason 1, N (%)				
	Reason 2, N (%)				
	Reason 3, N (%)				

Table 9 *The number of clinical PE (Pulmonary Embolism) events will be measured by spiral CT*

		Follow-up 1 (Day 1)	Follow-up 2 (Day 8)	Follow-up 3/ End of Study (Day 15)	p-value
Was a Spiral CT done?	Yes, N (%)				
	No, N (%)				
If “No”, please indicate a reason	Reason 1, N (%)				
	Reason 2, N (%)				
	Reason 3, N (%)				
Is the report interpreted, signed & dated by the PI or any of the designated site staff?	(Yes), N (%)				
	(No), N (%)				
If “No”, please indicate a reason:	Reason 1, N (%)				
	Reason 2, N (%)				
	Reason 3, N (%)				
If “Yes”, the report interpretation shows that the subject is:	Normal, N (%)				
	Abnormal, N (%)				
If abnormal, please state the reason:	Reason 1, N (%)				
	Reason 2, N (%)				
	Reason 3, N (%)				

Table 10 *Mean changes in Activated Partial Thromboplastin Time (APTT) where it will be done before first dose, 4 & 8 hours after first dose then on days 1,8,15 post operatively*

		Before 1 st dose	After 1 st dose		Post-operative			p- value
			4 h	8 h	Day 1	Day 8	Day 15	
Was an APTT test performed?	Yes, N (%)							
	No, N (%)							
If “No”, please indicate a reason	Reason 1, N (%)							
	Reason 2, N (%)							
	Reason 3, N (%)							
If “Yes”, the test result is	APTT; Mean ± SD (sec)							
APTT, % change								
p-value								
The test interpretation shows that the subject is:	Normal, N (%)							
	Abnormal, N (%)							
If abnormal, please state the reason:	Reason 1, N (%)							
	Reason 2, N (%)							
	Reason 3, N (%)							

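### The primary endpoint counts symptomatic thrombosis at any site, while the objective and sample size concern DVT and SAP Table 8 records only Doppler results

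*Protocol*

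**What the plan says.** The primary objective (protocol 5.1; the same in SAP 3.1) is "To evaluate the efficacy of Subcutaneous Thrombexx® ampoules (r-Hirudin RB variant 15 mg) in DVT prophylaxis post major orthopedic operations". The sample-size paragraph (protocol 17.1, SAP 8.1) calls its figure "sufficient to detect an incidence of 12.5% of DVT".

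The first primary endpoint is worded alike in the synopsis, protocol 8.1 and SAP 4.1. Protocol 8.1 opens "Primary end points included new onset symptomatic thrombosis requiring medical or surgical intervention or death due to thrombosis defined as fatal PE, ischemic" and runs on to the end of the list. The sentence has two limbs. One is new symptomatic thrombosis that needs treatment, with no site given. The other is "death due to thrombosis defined as fatal PE, ischemic stroke, mesenteric thrombosis, or myocardial infarction". Protocol 8.1 then lists PE as an item of its own: "The number of clinical PE events will be measured by spiral CT".

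The matching analysis variable (protocol 17.2.1, SAP 8.2.1) is "Proportion of patients experienced new onset symptomatic thrombosis". It does not mention veins, and it does not repeat the death limb.

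SAP Table 8 has the same title as that variable. Its opening row asks "Was a Routine bilateral compression Doppler done", and its only result row is Normal or Abnormal at days 1, 8 and 15. Table 9 has the same layout for spiral CT and PE.

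**The concern.** The primary proportion is the trial's main efficacy answer. A coronary or cerebral thrombosis after joint replacement does not show whether leg-vein thrombosis was prevented. Under the written rule it would still count against DVT prophylaxis, as would a death from stroke or myocardial infarction. With a single arm, no control group shows the background rate of such events.

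The planned table has a different fault. Doppler is routine at all three follow-up visits, so Table 8 will include DVTs without symptoms under a title that says symptomatic. It has no place for the deaths and arterial events that the endpoint names. An analyst cannot tell from the documents which of the two governs.

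**Working it through.** **1. The plan's own figure concerns DVT.** Inputs from protocol 17.1: p = 0.125, margin d = 0.05, 95% confidence (z = 1.95996).

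n = z²p(1−p)/d² = 3.8415 × 0.125 × 0.875 / 0.0025 = 168.06

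The stated 168 is reproduced. It is a precision calculation for a DVT incidence, not for the composite as written. The planned 100 does not follow from it, which is a separate matter.

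**2. What each place counts.**

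| Place | What is counted | Limited to venous events? |
|---|---|---|
| Objective (protocol 5.1, SAP 3.1) | DVT prophylaxis | Yes |
| Sample size (protocol 17.1, SAP 8.1) | DVT incidence, 12.5% | Yes |
| Scheduled efficacy assessments (protocol 7.1, 7.2) | DVT by Doppler, PE by spiral CT | Yes |
| Endpoint (synopsis, protocol 8.1, SAP 4.1) | Treated symptomatic thrombosis at any site; deaths from PE, stroke, mesenteric thrombosis or MI | No |
| Analysis variable (protocol 17.2.1, SAP 8.2.1) | New symptomatic thrombosis at any site | No |
| SAP Table 8 | Doppler Normal/Abnormal by visit | Yes, but with or without symptoms |

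No visit schedules an assessment for stroke, MI or mesenteric thrombosis. As planned, these would surface as adverse events (SAP Tables 12 and 13). A death would appear as a reason for discontinuation (SAP Table 20), without its cause.

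**3. Effect of one event.** Estimate = x/100. The exact (Clopper-Pearson) limits are the 2.5% quantile of Beta(x, 101−x) and the 97.5% quantile of Beta(x+1, 100−x).

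| Events x | Estimate | Exact 95% CI |
|---|---|---|
| 0 | 0% | 0 to 3.6% |
| 1 | 1.0% | 0.03 to 5.4% |
| 2 | 2.0% | 0.2 to 7.0% |
| 3 | 3.0% | 0.6 to 8.5% |

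Each added event moves the estimate by 1 point. Over this range the upper limit rises by about 1.5 to 1.8 points per event.

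**4. Comparison figures.** Protocol 4.2 cites 13 and 6 of 174 patients with overall and proximal DVT in a hip-replacement trial: 13/174 = 7.5% and 6/174 = 3.4%, printed there as 7 and 3 per cent. These figures and the 12.5% are given as DVT rates, not as rates of symptomatic DVT that needed intervention. Limiting the endpoint to venous events is therefore not enough for a comparison. DVTs found by Doppler without symptoms need their own row as well.

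**The case against.** An all-site composite can be a deliberate choice for an anticoagulant. The second trial cited in protocol 4.2, a multicentre study of desirudin, is reported there with a similar outcome of treated symptomatic thrombosis or death, and a venous-only primary moves away from it. This stands as a reason to keep the composite as a supportive row. It does not make the composite an answer to an objective stated as DVT prophylaxis.

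The plan is also descriptive. It sets no comparator or success threshold, and the intervals for 2 and 3 events overlap widely. That is true, and it limits the effect to what the reported proportion means. No pass or fail decision turns on it.

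A reader might infer that the list of four conditions defines the whole endpoint, so that a treated symptomatic DVT would not count. The documents do not support this. The list directly follows the words about death, so it naturally names causes of death. The analysis variable keeps symptomatic thrombosis without the list, and a treated DVT fits it plainly. Non-fatal PE is not lost either, because PE is a separate primary item with its own table.

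A reader might also infer that arterial events are certain to inflate the reported rate. Table 8 as drafted has nowhere to put them, and the first limb takes in an MI or stroke only if it is judged a new thrombosis. The conflict lies between the written rule and its table.

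**Conclusion.** The concern holds in this form: as written, the endpoint and the analysis variable do not measure the venous question that the trial asks, and SAP Table 8 does not tabulate the endpoint as written. The size is 1 percentage point per arterial event counted at n=100; for example, 2.0% (0.2 to 7.0) becomes 3.0% (0.6 to 8.5). The arithmetic assumes 100 analysed patients, each counted once. The documents give no rate for arterial events or for symptomatic venous events, so the share of the primary count that would be arterial cannot be derived from them. The mismatch does not depend on that share. The change should be made, although the composite is not invalid as a supportive outcome.

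**What to change.** - In the synopsis, protocol 8.1 and 17.2.1, and SAP 4.1 and 8.2.1, define one patient-level venous proportion with its 95% CI: symptomatic DVT requiring intervention, symptomatic non-fatal PE, or death due to PE.
- State that the list of conditions applies to deaths only, and mark every component as fatal or non-fatal.
- Report ischemic stroke, MI and mesenteric thrombosis separately, each with n and 95% CI. Flag venous mesenteric cases.
- Keep the all-site composite as a supportive row, for comparison with the desirudin trial cited second in protocol 4.2.
- Rebuild SAP Table 8 to show these components, with symptomless Doppler-detected DVT in its own row. Set that row and the symptomatic DVT row beside the 12.5%, 7% and 3% figures.

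Cost: edits to both documents and a few table rows, with no added patients or procedures. The case report form is not among the documents, so check that it records symptoms, intervention and cause of death. The adverse-event record in protocol 16.1 already asks for corrective treatment and outcome. The downside is a slightly smaller primary count. Make the change before database lock.
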